Upon consent, participants will be randomly assigned to Group #1 or Group #2. The study design is akin to a waitlist control design, with group #1 (treatment group) receiving 8 weeks of intervention followed by 8 weeks of continued use of TLC intervention tools, and group #2 (waitlist group) doing respite as usual for 8 weeks, followed by 8 weeks of more intensive coaching from the TLC intervention. Both group #1 and #2 will fill out daily/weekly reviews of their respite use throughout the calendar functions of the TLC intervention tools during the 16-week intervention period, as well as monthly questionnaires at baseline/enrollment, week 4, week 8, week 12, week 16, and week 20.

Note: when we created the online, self-administered version of the TLC intervention, we merged all data collection instruments with intervention prompts into a single online delivery package, so both group #1 and group #2 receive access to the TLC study tools from day 1 and end their access at the end of week 20. This has altered the traditional "waitlist" (i.e., no contact) condition associated with group #2. Both group #1 and group #2 receive the same instructions and orientation to the study on day 1. The groups differ only in the amount and type of "virtual coaching" (instructions and prompts from the TLC website) they receive at week 1 and week 9. Group #1 receives more intensive coaching at week 1, with an encouragement to continue doing it on their own at week 9. Group #2 receives less intensive coaching at week 1, with a more intensive coaching instructions presented to them at week 9.

Self-administered questionnaires and daily ecological momentary assessments (EMAs). Participants in both conditions will complete self-administered questionnaires at baseline, and then every 4 weeks thereafter (for a total of 6 questionnaires, spread across 20 weeks). All questionnaires will be distributed electronically via email. Responses will automatically be recorded in a secure REDCap data base.

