Participants are also asked to complete daily ecological momentary assessments (EMAs), in which they indicate if they used respite that day, and if so, their experienced and evaluative satisfaction with respite time-use. The daily EMAs will take about 1-2 minutes to complete as they are only 3 items (respite used [yes/no], and two items each measuring experienced and evaluative time-use satisfaction). The caregivers will be prompted weekly to complete their EMAs. Note: as mentioned above, all EMA data collection has been

integrated into the online version of the TLC intervention tools through a digital calendar, combining the TLC intervention with the collection of daily EMA.

Each questionnaire will take about 10-45 minutes to complete. The baseline and final questionnaire are significantly longer than the monthly questionnaires (i.e., 10 minutes versus 45 minutes). Questionnaires will include standardized fixed-choice and open-ended survey questions related to :

- demographic indicators
- caregiving context, and
- caregiver health and well-being (i.e., burden, anxiety, positive affect, global health).

The final questionnaire includes additional measures related to the participants' use of the TLC intervention tools. We will assess their perceptions of feasibility, usability, and acceptability of the online version of the TLC intervention. Other feasibility indicators such as login behavior, intervention protocol completion, and dosage will be imported in real-time directly from google analytics into the secure REDCap data base.

Procedures performed for research purposes only:

[figure not shown]
Statistical Methods, Data Analysis and Interpretation

STATISTICAL DESIGN & POWER

The overall project has three specific aims. This application relates to Aim 2, where which entails human subjects research.

Aim 2: Conduct a hypothesis driven pilot test of the TLC intervention with dementia caregivers

Statistical Design & Power - Aim 2

The purpose of Phase 2 is to conduct a fully-powered pilot study to measure feasibility and efficacy of the TLC intervention with a sample of dementia caregivers (n=120). This section describes the planned analyses to assess efficacy of the TLC intervention.

Study Design

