Because this is part of early-stage intervention development activities (Stage 1), we have designed a clinical trial to pilot-test feasibility as well as efficacy of the redeveloped TLC intervention. We propose to use a waitlist control cohort design, using a fully powered sample to provide the most rigorous analysis possible. The waitlist design allows all participants to receive the intervention. As shown here in the figure, participants will be randomized to one of two sequences. After baseline data collection and an initial orientation/control period for the first 4 weeks, Group A will have 8 weeks of TLC intervention, then 8 weeks of follow-up. Group B will have 8 weeks of waitlist control, and then TLC intervention for 8 weeks, beginning at week 12. We will use ecological momentary assessment (EMA) during the entire 20-week study period to capture daily time-use trends for any respite periods received (n=140 daily reports, max). EMA aims to minimize recall bias and maximize ecological validity. Primary outcomes data will be collected via electronically administered surveys at baseline (T0) and every 4 weeks thereafter (T4, T8, T12, T16, T20), for a total of 6 assessments. This randomized, prospective, and longitudinal design

allows each participant to serve as its own control and offers opportunities to assess both within- and between-group differences over time (Group A vs. B).

Measures

The primary outcome is wellbeing, measured with two standardized scales indicating “caregiver burden” and “anxiety.” The mechanism driving the intervention effect is theorized to be related to respite time-use and time-use satisfaction. This construct is measured with “experienced” and “evaluative” time-use measures.

Analysis

The analysis to test for efficacy will specifically look at treatment x time interaction that combines both vertical (between individuals at given timepoints) as well as horizontal (evolution within individual over time) comparisons. We will utilize a multilevel model that consists of level 1 (within person) and level 2 (between person). Thus, the overall composite two level Multi-Level Mixed effects Model (MLM) is defined as follows with the first set of brackets representing fixed effects and second set random effects:

$$Y_{ij} = [\beta_0 + \beta_1 T_j + \beta_2 X_{ij}] + [\zeta_{0i} + \zeta_{1i} T_{ij} + \epsilon_{ij}] \quad [\text{equation 1}]$$

[figure not shown]

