where Y_{ij} is the outcome measure (Caregiver Burden and Anxiety) for participant (i) at time (j) where j is an indicator for time (baseline, 4 weeks, 8 weeks, 12 weeks, 16 weeks and 20 weeks). β_0 is the population mean level of the outcome measure prior to the TLC intervention, β_1 fixed effect for time independent of intervention, X_{ij} is the intervention status (pre-TLC or Post-TLC/Follow-up) at timepoint j, and β_2 is the intervention treatment effect. Random effects include individual-level intercept (ζ_{0i}), individual-level slope of change over time ($\zeta_{1i} T_{ij}$), and ϵ_{ij} for residual error of each outcome measure. Our hypotheses for Aim 2 are summarized here:

Over time, we expect intervention engagement to produce more positive wellbeing, with time satisfaction as the mechanism through which TLC achieves its effect.

- H1:** Burden & anxiety will be lower among the treatment group compared to those in control/waitlist condition (direct effect)
- H2:** Time-use satisfaction will be higher among the treatment group compared to those in control/waitlist (direct effect)
- H3:** Higher time-use satisfaction will be associated with lower burden & anxiety (direct effect)
- H4:** Higher time-use satisfaction will mediate the effect of the intervention on burden and anxiety (direct & indirect effect)

H1: Burden & anxiety will be lower among the treatment group compared to those in control/waitlist condition (direct effect)

Figure 2: Anticipated results for Wellbeing with TLC

Our primary outcome will test the hypothesis that there will be significant change in “caregiver burden” or “anxiety” immediately post intervention. Figure 2 shows the anticipated results with no change during the run-in period, increase in wellbeing in Group A during the intervention but not WLC. Group B then shows increased wellbeing during TLC, with Group A maintaining or slight decrease in “caregiver burden” or “anxiety” over time. With the planned 120 participants (60 per group), we will be able to detect small to medium effect sizes on the two outcomes with greater than 90% Power (see below). Intent-to-treat analyses (ITT) will be performed on non-completers using a terminal score for both “caregiver burden” and “anxiety” scores.

H2: Time-use satisfaction will be higher among the treatment group compared to those in control/waitlist (direct effect)

[figure not shown]

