When substituting the Mediator M in equation 3 the indirect pathway by which the TLC intervention impacts wellbeing through time-use is represented by the product of coefficients $a \cdot b$. If significant, then mediation is present. If the direct pathway c in equation 3 becomes non-significant in equation 4 (c') when conditioning on the indirect pathway, then M is said to fully mediate the relationship between TLC and wellbeing. Importantly, in the models we will control for individual values of the wellbeing outcomes obtained before the start of the TLC intervention. The indirect pathway will be tested using the Sobel test that divides product-of-coefficients $a \cdot b$ by the first-order delta-method standard error of the indirect effect. This value is compared against a standard normal distribution to test for significance.¹⁴⁸ We will also consider additional statistical mediation tests that account for non-normality of the product of coefficients and/or bootstrapping methods for more accurate estimates.¹²¹

Although not stated as distinct hypotheses, we will conduct additional exploratory analyses to further explain for whom and how the intervention achieves its effect. These analyses will be guided by the following questions: Do variations in the receipt of the intervention modify these relationships? For example, do participants that report higher intervention feasibility (i.e., higher satisfaction and usability of the tool) or higher dosage (i.e., they accessed more of the intervention's features) show stronger treatment effects? This will be assessed by replacing the dichotomous intervention variable X (TLC vs. WLC) in equation 1 with measures indicating dosage or perceived feasibility. Similarly, we will explore whether individual characteristics or circumstances modify the relationship between intervention, time-use satisfaction, and wellbeing over time. Here, we will use biologic variables of gender and age as well as measures that capture changes in the context of the caregiving relationship as both control variables and interaction. Finally, we will explore whether treatment effects maintain, attenuate, or no-change once the intervention period ends. This will be assessed using a repeated-measures design using Group A's data from immediately post-intervention through the 8-week follow-up period.

Power and Sample Size

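### Replacing X with dosage or perceived feasibility in equation 1 cannot show who has stronger treatment effects, and can give a significant coefficient when TLC has no effect

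*Combined protocol and SAP*

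**What the plan says.** The paragraph after the H4 mediation text opens: "Although not stated as distinct hypotheses, we will conduct additional exploratory analyses". Its first question is: "Do variations in the receipt of the intervention modify these relationships". It gives as an example whether participants with higher satisfaction and usability, or with higher dosage, have stronger treatment effects. The method follows: "This will be assessed by replacing the dichotomous intervention variable X (TLC vs. WLC) in equation 1 with measures indicating dosage or perceived feasibility".

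Four other places define the pieces:

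- **X.** Under Analysis, "X_{ij} is the intervention status (pre-TLC or Post-TLC/Follow-up) at timepoint j". X varies over time within a caregiver.
- **Randomisation.** Under Study Design, "participants will be randomized to one of two sequences". The sequence sets when X switches.
- **Dosage.** Figure 4 counts log-ins, and the exploratory paragraph refers to features accessed. Both are use that the caregiver chooses. The note on the waitlist condition under Procedures says "both group #1 and group #2 receive access to the TLC study tools from day 1", so use is possible before intensive coaching.
- **Perceived feasibility.** Under Procedures, "The final questionnaire includes additional measures related to the participants' use of the TLC intervention tools", followed by self-reported feasibility, usability and acceptability.

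The exploratory paragraph plans interaction terms for gender, age and changes in caregiving context. It plans none for dosage or feasibility. Adjustment for pre-intervention outcome values is stated only for the mediation models.

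**The concern.** The question concerns effect modification: is the TLC effect larger in some caregivers than in others? Answering it takes a treatment contrast and a term that lets the contrast vary. The stated model drops the first and does not add the second.

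What replaces X is self-selected. Caregivers with less burden, or whose burden is improving, may use the tool more or rate it higher. A rating taken at the end can also follow from the outcome rather than precede it. Either would produce an association between engagement and burden with no help from TLC.

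This is Stage 1 work meant to shape later versions of the tool, and feasibility is named as another primary outcome. A coefficient taken for a dose-response could influence that development.

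**Working it through.** **What the model estimates.** A model for effect modification by M would be

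Y = β0 + β1·T + β2·X + β3·M + β4·X·M + random terms,

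with the claim resting on β4. The planned model is

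Y = β0 + β1·T + γ·D + random terms,

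where D is dosage or feasibility. It has neither β2 nor β4. Two cases:

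- D is one rating per caregiver. Then γ compares caregivers with high and low ratings at all six assessments, including baseline. No pre/post-TLC contrast is left.
- D is X multiplied by the caregiver's dose. Then γ does use the randomised timing, but a TLC effect identical for everyone would also make γ non-zero. A significant γ does not show that heavier users benefit more.

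**Inputs from the plan.** 60 per sequence (120 in all), 6 assessments from T0 to T20, random intercept and slope. The 0.05 level is stated only for the mediation power and is taken as two-sided. The plan gives no operating figure for this analysis, so there is none to reproduce.

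**Assumed, because the plan gives no values.** Variances: intercept 0.5, slope 0.01 per 4-week step, residual 0.4. Dose is scaled to mean 1 with SD 0.5 between caregivers. The correlation of engagement with the caregiver's underlying burden level or slope runs from 0 to -0.5. The TLC effect is zero. Estimation is by generalised least squares with the true covariance, 2000 runs per setting. At a true 5% the simulation standard error is √(0.05 × 0.95 / 2000) = 0.5 percentage points.

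**Rejection rate with no TLC effect, X replaced by:**

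| Correlation of engagement with burden | (a) constant per-person rating or total dose | (b) dose, zero before TLC | (c) dose, half-level use before intensive coaching |
|---|---|---|---|
| 0 | 4-6% | 4-6% | 4-6% |
| -0.2, level | 50% | 7% | 9% |
| -0.3, level | 85% | 11% | 16% |
| -0.5, level | 100% | 21% | 38% |
| -0.3, slope only | 11% | 15% | 15% |
| -0.3, level and slope | 96% | 35% | 50% |

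In (c), dose is zero at T0 and half-level from then until intensive coaching starts. With X kept, the rate is 4.0% to 6.4% in every setting. Nearly all the excess rejections point to apparent benefit.

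**Hand check of (a).** With T = 0 to 5 (mean 2.5), the mean of a caregiver's six outcomes has variance 0.5 + 2.5² × 0.01 + 0.4/6 = 0.629, SD 0.793. The level has SD √0.5 = 0.707. A correlation of size 0.2 with level becomes 0.2 × 0.707/0.793 = 0.178 with the observed mean. A correlation of size 0.3 becomes 0.267. Rejection is about Φ(atanh(r) × √117 − 1.96):

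- 0.2: Φ(0.180 × 10.82 − 1.96) = Φ(−0.01) = 0.50
- 0.3: Φ(0.274 × 10.82 − 1.96) = Φ(1.00) = 0.84

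These agree with 50% and 85%.

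**Check with a fitted mixed model (60 runs per setting, so rough).** At correlation 0: X kept 5%, (a) 3%, (b) 3%. At -0.3 with level: X kept 8%, (a) 83%, (b) 12%.

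**Timing.** The table uses the Procedures timing (intensive coaching at week 1 or week 9). Study Design has a 4-week run-in, with Group B starting at week 12. Under that timing (1000 runs), the -0.3 level-and-slope row is 95%, 27% and 56%. The conclusion is the same.

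**The case against.** The strongest case on the other side has four parts.

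1. **The analysis is exploratory.** This stands. H1 to H4, the sample size and the Figure 4 benchmarks do not depend on it. The label limits the harm, but it does not make the model answer its question.

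2. **The high rates come from one coding.** This stands in part. The plan does not say how D is coded before TLC, and zero before TLC is a natural choice because X is time-varying. At correlations of -0.2 to -0.3 with level, that coding rejects 7-11% of the time, not 50-85%. A rating tied to the final questionnaire, however, has no natural pre-TLC value.

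3. **An assumed association is bound to be detected.** This is true, and at zero correlation there is no inflation. A reader might quote Fisher-z figures of 59% and 92% for correlations of 0.2 and 0.3 at N = 120. Those are only the power to detect an assumed correlation with one outcome per person, not error rates of equation 1. The fault lies in reading the association as a treatment effect.

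4. **Dosage follows the randomised coaching schedule.** This stands. A reader might infer that the dosage coefficient holds no randomised information. The documents do not support that, because the groups receive different coaching at set times and use may follow it. The coefficient holds randomised and self-selected information mixed together.

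A reader might also infer that feasibility is asked only at the end. The plan says that the final questionnaire includes these measures. It does not say that no other questionnaire does.

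**Conclusion.** The point holds for the dosage and feasibility analyses as written. With X replaced and no interaction, they cannot show effect modification, and they can be significant when TLC does nothing. The first conclusion follows from the form of the model and needs no assumed values.

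The second depends on values that the plan does not give. Inflation ranges from none, when engagement is unrelated to the course of burden, to near certainty for a constant rating with a moderate correlation. For time-varying dose it is modest at correlations of -0.2 to -0.3 with level, and larger if use also tracks the slope. If more burdened caregivers use the tool more, the bias runs the other way and could hide a benefit. Adjusting for baseline burden would reduce confounding by level. It would not remove confounding by slope or reverse causation from late ratings.

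The consequence is a misleading exploratory statement. The documents give no ground for extending the criticism to the primary efficacy test.

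**What to change.** Change the exploratory paragraph as follows:

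- Keep X, with timing set by the randomised sequence, as the treatment term in equation 1.
- Report dosage and perceived feasibility as descriptive associations with outcome, and state how each is coded before TLC.
- Delete the reading as stronger treatment effects.
- Limit effect-modification claims to baseline characteristics, through X-by-characteristic terms. Gender and age fit this. For caregiving context, it means the baseline value, not the change during the study.

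The cost is a few sentences of SAP text and the loss of a dose-response claim that the design does not support in this form.

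An instrumental-variable estimate per unit of dose, with randomised group as instrument, is optional and not part of this fix. It answers a different question: the average effect per unit of dose, not who benefits more. It needs a stated exclusion assumption, which is doubtful for log-in counts because the groups differ in the type as well as the amount of coaching. It also needs a check of instrument strength, since both groups use the same calendar from the start. Procedures and Study Design would first have to be reconciled on when Group B's intervention begins.

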Scientific Premise - An important element missing from the research on respite's effectiveness is how caregivers use their respite time. Congruence between desired and actual time use has been identified as a predictor of overall life satisfaction.⁵¹ Our previous research suggests that if caregivers are able to make respite more effective and have higher levels of respite time-use satisfaction, they will enhance their wellbeing and prevent further burnout, enabling them to continue in their role as caregivers for longer periods of time. An expert panel sponsored by ARCH (a federally-funded national respite network and resource center) recently summarized the state of research on respite and provided guidelines for future research;^{52 53} their recommendations included finding ways to make respite more effective. Any intervention designed to maximize the benefits of respite, or to support AD/ADRD caregivers in general, needs to be cost-effective, scalable, individually tailored to caregivers' needs, and readily available no matter where caregivers reside, such as in rural areas.^{48,54,55} Consistent with a recommendation of the NIH AD Research Summit in 2015,⁵⁶ these goals may be best achieved by delivering interventions using widely available mobile and internet technologies.

The Phase 1 study was deemed Non Human Subjects Research.

Phase 3 will not be conducted under this IRB application.

Purpose and Objectives

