Aim 3 is intended to explore future implementation of the redeveloped TLC intervention with respite providers. This provides yet another layer of the tool's feasibility. We will host webinars to demonstrate the features and functionality of the TLC intervention as well as to preview pilot study results from Aim 2, then ask providers for feedback on their likelihood of implementation and barriers to using TLC with their clients.

Together, these three aims represent a comprehensive approach to Stage 1 research activities, with the overall goal of developing an intervention that is scalable to real world applications. Throughout all stages of the proposed project, our team is committed to community-engaged research practices, where community partners will provide input and connect us with potential research participants. Given this pragmatic yet scientifically rigorous approach, the results have the potential to guide and accelerate the eventual implementation of the TLC intervention to community and health care practice.

This application relates specifically to Phase 2 of the project, which specifically addresses Aim 2 where human subjects will be recruited and enrolled.

Study Population

Age of Participants: Over 18 years of age

Sample Size:

At Utah: 150
All Centers: 150

Inclusion Criteria:

Inclusion criteria:

AD/ADRD caregivers who are currently using or interested in using respite, such as home-care respite providers or adult daycare providers, or informally provided by family members or friends.

The caregiver must:

- 1) be the primary caregiver,
- 2) live in the same house with the care recipient,
- 3) have access to and/or interest in using respite at least once a week for a minimum of 4 hours,
- 4) be providing care to a family member with Alzheimer's disease or dementia,
- 5) be English speaking, and
- 6) be age 18 or over.

We will recruit a total of 150 caregivers with purposive selection of caregivers to ensure that we are getting a diverse sample of caregivers (i.e., males and females, racial and ethnic diversity, rural and urban residence, early and late-stage dementia caregivers).

Exclusion Criteria:

- Not a primary caregiver
- Not living in the same house with the care recipient
- No access and/or interest in using respite at least once a week for a minimum of 4 hours
- <18 years of age
- Non-English speaking
- Not providing care to a family member with Alzheimer's disease or dementia

Design

Randomized Trial

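### The exploratory for-whom analyses use caregiving changes that arise after randomisation as control variables and moderators, so those models do not estimate the total effect of assignment to TLC

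*Combined protocol and SAP*

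**What the plan says.** After the mediation section for H4, the plan announces that "we will conduct additional exploratory analyses to further explain for whom and how the intervention achieves its effect". One of these analyses is described as follows: "we will explore whether individual characteristics or circumstances modify the relationship between intervention, time-use satisfaction, and wellbeing over time". For this it will use gender and age together with "measures that capture changes in the context of the caregiving relationship as both control variables and interaction". No other use of the change measures is stated, and they are not named. The Procedures section lists caregiving context as a questionnaire domain but gives no items.

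The Scientific Premise says that more effective respite should improve wellbeing and prevent burnout, "enabling them to continue in their role as caregivers for longer periods of time". The Inclusion Criteria require the caregiver to "live in the same house with the care recipient", a condition that can end during follow-up.

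The confirmatory models are different. In equation 1 the fixed effects are an intercept, time and intervention status, where "X_{ij} is the intervention status (pre-TLC or Post-TLC/Follow-up) at timepoint j". H2 uses the same model and H3 the same framework with time-use satisfaction as predictor. For H4 the only control named is a pre-intervention one: "in the models we will control for individual values of the wellbeing outcomes obtained before the start of the TLC intervention".

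**The concern.** Gender and age are fixed before assignment and are safe as covariates. A change in the caregiving relationship is recorded during follow-up, and on the plan's own premise TLC may influence some such changes. The sentence treats the two kinds of variable alike.

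Two things are at stake. First, once a variable that assignment can affect is held constant, the coefficient for intervention omits whatever works through that variable. If an unmeasured cause drives both the change and the outcome, the coefficient can also show an effect where none exists. Second, a subgroup defined by a post-randomisation change is partly a product of the intervention. An interaction with it mixes consequences of TLC with characteristics of caregivers, so it does not answer the question of who benefits.

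In addition, no section compares these changes between the randomised groups. A shift in them, welcome or not, would appear only as a model term.

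**Working it through.** The plan states no figure on this point, so there is none to reproduce. The check has three parts.

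**1. Which models are affected.**
- H1, equation 1: intercept, time, intervention status. No caregiving-change term.
- H2 and H3: same model or framework. No caregiving-change term named.
- H4: pre-intervention wellbeing only.
- Exploratory for-whom analyses: caregiving changes as control and as interaction.

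Only the last group is affected.

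**2. How far adjustment could move an estimate.** The Power section gives a burden effect of 4 to 6.5 points. The event rates and the effect *g* of an event on burden are not in the documents and are assumed here. With no shared cause and no interaction, the part removed by adjustment is

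(p_TLC − p_control) × *g*.

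- Smallest case, 5% control versus 2.5% TLC, |*g*| = 5: 0.025 × 5 = 0.125 point. This is 0.125/4 = 3% or 0.125/6.5 = 2% of the planned effect.
- Middle case, 10% versus 5%, |*g*| = 10: 0.05 × 10 = 0.5 point, or 0.5/4 = 12.5% and 0.5/6.5 = 8%.
- Largest case, 20% versus 10%, |*g*| = 10: 0.10 × 10 = 1.0 point, or 1.0/4 = 25% and 1.0/6.5 = 15%.

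The sign follows *g*. A simulation of the largest case (60 per group, assumed SD 10, direct effect −4, 2000 runs) gave:
- event raises burden by 10: unadjusted −4.98, adjusted −3.99, so the benefit looks smaller after adjustment;
- event lowers burden by 10: unadjusted −2.96, adjusted −3.96, so the benefit looks larger.

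A shared unmeasured cause adds a second route. Suppose TLC shifts the change measure by 0.2 to 0.5 residual SD and has no effect on burden, while an unmeasured stressor acts on both with coefficient 0.5 (all assumed). The slope of burden on the change measure is then 0.5 × 0.5 = 0.25. The adjusted model shows a false effect of 0.2 × 0.25 = 0.05 to 0.5 × 0.25 = 0.125 units, about 0.06 to 0.14 of the outcome SD of roughly 0.86 in that simulation.

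**3. Whether the events could be tested between groups.** With 60 per group (the planned final sample of 120), two-sided 0.05 and the same assumed rates:

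| Control vs TLC | Power | Per group for 80% power |
|---|---|---|
| 5% vs 2.5% | 11% | 906 |
| 10% vs 5% | 18% | 435 |
| 20% vs 10% | 33% | 199 |

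A comparison can therefore only be descriptive.

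**The case against.** The strongest reply is that no hypothesis test uses these covariates. The paragraph is labelled exploratory, the unadjusted effect is still estimated, and this is a Stage 1 pilot. That stands, and it confines the point to one paragraph.

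The premise is also weaker than it may look. The Scientific Premise places staying in the role after improved wellbeing, as a later consequence. It is not among H1 to H4, the stated mechanism is time-use satisfaction, and the treatment-versus-waitlist contrast lasts 8 weeks. Any shift in caregiving may therefore be small. Because the measures are unnamed, some may reflect disease course, which the documents nowhere say TLC would alter; exploring those is reasonable. All of this stands as a limit on size. It does not make a post-randomisation change equivalent to gender or age, and the plan does not separate changes that TLC could affect from those it could not.

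Figure 5 (RE-AIM) plans to describe attrition, to explore missing data as a moderator, and asks about unintended outcomes. That is partial cover only. Attrition is a different event, and the analysis named for unintended outcomes is the set of Aim 2 hypothesis tests, which cover burden, anxiety and time-use satisfaction.

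A reader might infer that part of TLC's effect is adjusted away in the trial's main result. The documents do not support this: equation 1 has no such term, and even in the exploratory models adjustment could enlarge the apparent benefit.

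**Conclusion.** The point holds for the exploratory for-whom analyses only. As written, those models condition on changes that assignment may affect. Their intervention coefficients do not estimate the total effect of assignment, and their interactions cannot be read as showing who benefits. The primary H1 analysis is untouched.

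The size cannot be derived from the documents. Under the assumed rates and event effects, the shift from the removed path is 0.125 to 1.0 burden point in either direction, or 3% to 25% of a 4-point effect and 2% to 15% of a 6.5-point effect. The true shift could be smaller if TLC barely alters caregiving within 8 weeks, or if the unnamed measures mainly track disease course. This is an inexpensive improvement to an exploratory section and no threat to the trial's main conclusion.

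**What to change.** In the exploratory paragraph at the end of the H4 section:

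- Name the caregiving-context measures. Restrict control variables, and the moderators used for for-whom conclusions, to values recorded at T0: gender, age and baseline caregiving context.
- If changing circumstances are still explored, label those models as descriptive and as not estimating the total effect of assignment.
- Report whatever caregiving-context changes the surveys record, by randomised group and survey interval, as counts or means with differences and confidence intervals and no powered test. Limit the TLC-versus-waitlist reading to the period before Group 2's intensive coaching. Procedures places that start at week 9 and the Study Design section at week 12; the two must be reconciled before the table is laid out.
- Keep surveys completed after such a change in the main analysis. Leaving them out would condition on the same kind of post-randomisation event, so it could serve only as a labelled sensitivity description.

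The cost is SAP wording and one table, from whatever change measures the surveys carry. The downside is slightly less residual variance explained in an exploratory model, and changing circumstances can be explored only descriptively.
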